### 6.7.4.2. Hematology/Blood chemistry

**Table 13 Hematology/biochemistry read-outs**

Blood sampling timepoint		Study groups	Number of subjects	Component
Type of contact and timepoint	Sampling timepoint			
Screening #1	SCR#1	P-Fx NP-Fx	~40**	HIV IgG + Ag HBsAg Ab HCV Ab Hemoglobin Leukocytes (WBC) Platelets
Screening #2	SCR#2			ALT AST Creatinine
Visit 1 (Day 1) Visit 2 (Day 8)	Vaccination day Post-vaccination			Hemoglobin Leukocytes (WBC) Platelets
Visit 3 (Day 22) Visit 22 (Day 50) Visit Par*	Post-challenge Post-challenge	All subjects	~64	ALT AST Creatinine

**HIV** = human immunodeficiency virus; **IgG** = immunoglobulin G; **Ag** = antigen; **HBsAg** = hepatitis B surface antigen; **Ab** = antibody; **HCV** = hepatitis C virus; **WBC** = white blood cell; **ALT** = alanine aminotransferase; **AST** = aspartate aminotransferase

\*Biochemistry and hematology parameters will be collected the day of first parasitemia (between Visit 4 [Day 27] and Visit 21 [Day 48]).

\*\*A minimum of 20 subjects per group (P-Fx and NP-Fx) is anticipated

**6.7.4.3. Parasitemia****Table 14 Parasitemia read-outs**

Blood sampling timepoint	Study groups	Number of subjects	Component	Components priority rank
Visit 4 (Day 27)				
Visit 5 (Day 28)				
Visit 6 (Day 29)				
Visit 7 (Day 30)				
Visit 9 (Day 32)				
Visit 8 (Day 31)				
Visit 10 (Day 33)				
Visit 11 (Day 34)				
Visit 12 (Day 35)				
Visit 13 (Day 36)	All subjects	~64	Blood smear	1
Visit 14 (Day 37)				
Visit 15 (Day 38)				
Visit 16 (Day 39)				
Visit 17 (Day 40)				
Visit 18 (Day 42)				
Visit 19 (Day 44)				
Visit 20 (Day 46)				
Visit 21 (Day 48)				
Visit 22 (Day 50)				

PCR = polymerase chain reaction

In case of insufficient blood sample volume to perform assays for parasitemia assessment, samples will be analyzed according to priority ranking provided in [Table 14](#).

**6.7.5. Immunological correlates of protection**

No correlate of protection has been demonstrated so far for the CS antigen.

For the HBsAg, the conventional correlate of protection is anti-HBs antibody concentrations above 10 mIU/mL [[European Consensus Group on Hepatitis B Immunity, 2000](#)].

The investigator is encouraged to share the immunological assay results for non-responders with the study subjects.

For the subjects identified as non-responders, it remains the responsibility of the investigator in charge of the subject's clinical management to determine the medical need for re-vaccination and to re-vaccinate the subjects as per local/regional practices.

## 7. STUDY VACCINE AND ADMINISTRATION

### 7.1. Description of study vaccine

The candidate RTS,S/AS01 vaccine to be used has been developed and manufactured by GSK Biologicals.

The Quality Control Standards and Requirements for the candidate vaccine are described in separate Quality Assurance documents (e.g., release protocols, certificate of analysis) and the required approvals have been obtained.

The vaccine is labelled and packed according to applicable regulatory requirements.

**Table 15 Study vaccine**

Treatment name	Vaccine name	Formulation	Presentation	Volume to be administered*	Number of doses
RTS,S/AS01 E (1/5 th dose)	RTS,S	RTS,S=25µg	Lyophilized pellet in a glass vial	0.1 mL	1
	AS01E	MPL=25µg; QS21=25µg; Liposomes	Liquid solution in a glass vial		

**MPL** = Monophosphoryl lipid; **QS-21** = *Quillaja saponaria* Molina, fraction 21 (Licensed by GSK from Antigenics Inc., a wholly owned subsidiary of Agenus Inc., a Delaware, USA corporation)

\*After reconstitution

### 7.2. Storage and handling of study vaccine

The study vaccine must be stored at the respective label storage temperature conditions in a safe and locked place. Access to the storage space should be limited to authorized study personnel. The storage conditions will be assessed during pre-study activities under the responsibility of the sponsor study contact. The storage temperature should be continuously monitored with calibrated (if not validated) temperature monitoring device(s) and recorded. Refer to the Module on Clinical Trial Supplies in the SPM for more details on storage of the study vaccine.

Temperature excursions must be reported in degree Celsius.

Any temperature excursion outside the range of 0.0°C to +8.0°C/+32°F to +46°F (for +2°C to +8°C/+36°F to +46°F label storage condition) impacting investigational medicinal products (IMPs) must be reported in the appropriate (electronic) temperature excursion decision form. The impacted IMPs must not be used and must be stored in quarantine at label temperature conditions until usage approval has been obtained from the sponsor.

Refer to the Module on Clinical Trial Supplies in the SPM for details and instructions on the temperature excursion reporting and usage decision process, packaging and accountability of the study vaccine.

### 7.3. Dosage and administration of study vaccine

In this study, the commercial presentation of RTS,S/AS01E will be used, i.e., a glass vial of lyophilized RTS,S antigen to be reconstituted with a glass vial of AS01E Adjuvant System. A full dose of RTS,S/AS01E (0.5 mL) contains 25 µg of the RTS,S antigen and 25 µg of each immunostimulant MPL and QS-21.

From the reconstituted vaccine vial, 0.1 mL will be withdrawn to administer a Fx booster dose of RTS,S/AS01E.

**Table 16 Dosage and administration**

Type of contact and timepoint	Study group	Treatment name	Volume to be administered	Route	Site	
					Location	Laterality*
Visit 1 (Day 1)	P-Fx NP-Fx	RTS,S/AS01 E (1/5 th dose)	0.1 mL	IM	Deltoid	Non-Dominant

IM: intramuscular

\*The non-dominant arm is the preferred arm of injection. In case it is not possible to administer the vaccine in the non-dominant arm (e.g., in case of skin alterations due to tattoos, rashes, burns or other skin disorders subject to the discretion of the investigator), an injection in the dominant arm may be performed.

### 7.4. Replacement of unusable vaccine

In addition to the vaccine doses provided for the planned number of subjects (including over-randomization when applicable), at least 10% additional vaccine doses will be supplied to replace those that are unusable.

### 7.5. Contraindications to vaccination

The following event constitutes contraindications to administration of RTS,S/AS01E at that point in time; if this event occurs at the time scheduled for vaccination, the subject may be vaccinated at a later date, within the time window specified in the protocol (see Section 6.5), or the subject may be withdrawn at the discretion of the investigator (see Section 9.5):

- Acute disease and/or fever at the time of vaccination.
  - Fever is defined as temperature  $\geq 37.5^{\circ}\text{C}/99.5^{\circ}\text{F}$ . The preferred location for measuring temperature in this study will be the oral cavity.
  - Subjects with a minor illness (such as mild diarrhea, mild upper respiratory infection) without fever can be administered the vaccine.

## 7.6. Concomitant medications/products and concomitant vaccinations

At each study visit, the investigator or delegate should question the subject about any medications/products taken and vaccinations received by the subject.

### 7.6.1. Recording of concomitant medications/products and concomitant vaccinations

The following concomitant medication(s)/product(s)/vaccine(s) must be recorded in the eCRF:

- All concomitant medications/products, except vitamins and dietary supplements, administered during the period within seven days following Day 1 (Day 1 to Day 8) and during the entire sporozoite challenge (Day 22 to Day 50).
- Any concomitant vaccination administered in the period starting seven days before Day 1 and ending at the last study visit (Day -7 to Day 190).
- Prophylactic medication (i.e., medication administered in the absence of ANY symptom and in anticipation of a reaction to the vaccination) (for P-Fx and NP-Fx groups).

E.g., an anti-pyretic is considered to be prophylactic when it is given in the absence of fever and any other symptom, to prevent fever from occurring (fever is defined as temperature  $\geq 37.5^{\circ}\text{C}/99.5^{\circ}\text{F}$  regardless the location of measurement). The preferred location for measuring temperature in this study will be the oral cavity.

- Any concomitant medications/products/vaccines listed in Section 7.6.2.
- Any concomitant medications/products/vaccines relevant to a SAE/pIMD to be reported as per protocol or administered at any time during the study period for the treatment of a SAE/pIMD. In addition, concomitant medications relevant to SAE(s) and pIMD(s) need to be recorded on the expedited Adverse Event report.

### 7.6.2. Concomitant medications/products/vaccines that may lead to the elimination of a subject from Per-Protocol analyses

The use of the following concomitant medications/products/vaccines will not require withdrawal of the subject from the study but may determine a subject's evaluability in the Per-Protocol analysis. See Section 11.5 for cohorts to be analyzed:

- Any investigational or non-registered product (drug or vaccine) other than the study vaccine used during the study period.
- Immunosuppressants or other immune-modifying drugs administered chronically (i.e., more than 14 days in total) during the study period. For corticosteroids, this will mean prednisone  $\geq 20$  mg/day, or equivalent. Inhaled and topical steroids are allowed.
- Long-acting immune-modifying drugs administered at any time during the study period (e.g., infliximab).

- A vaccine not foreseen by the study protocol administered during the period starting seven days before dose and ending seven days after the dose of vaccine administration\*.

\*In case an emergency mass vaccination for an unforeseen public health threat (e.g., a pandemic) is organized by the public health authorities, outside the routine immunization program, the time period described above can be reduced if necessary for that vaccine provided it is licensed and used according to its Summary of Product Characteristics or Prescribing Information and according to the local governmental recommendations and provided a written approval of the Sponsor is obtained.

Although vaccination with routine recommended national vaccination such as with the influenza or pneumococcal vaccines will not lead to elimination, every effort should be made to have the vaccinations occurring either more than seven days before vaccination or more than seven days after vaccination.

- Immunoglobulins and/or any blood products administered during the study period.
- Drugs known to have anti-*Plasmodium* properties, used during the challenge period before identification of parasitemia.

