### 5.3. Exclusion criteria for enrollment

Deviations from exclusion criteria are not allowed because they can potentially jeopardize the scientific integrity, regulatory acceptability of the study or subject safety. Therefore, adherence to the criteria as specified in the protocol is essential.

The following criteria should be checked at the time of study entry. If ANY exclusion criterion applies, the subject must not be included in the study:

For all subjects except the infectivity control subjects:

- Any medical condition that in the judgment of the investigator would make intramuscular injection unsafe.
- History of any reaction or hypersensitivity likely to be exacerbated by any component of the vaccine.
- History of anaphylaxis post-vaccination.

For all subjects:

- Use of any investigational or non-registered product (drug or vaccine) other than the study vaccine during the period starting 30 days before Day 1 (Day -29 to Day 1) (for P-Fx and NP-Fx groups)/before the malaria challenge (for infectivity control subjects), or planned use during the study period.
- Chronic administration (defined as more than 14 days in total) of immunosuppressants or other immune-modifying drugs during the period starting six months prior to Day 1 (for P-Fx and NP-Fx groups) or malaria challenge (for infectivity control subjects). For corticosteroids, this will mean prednisone  $\geq 20$  mg/day, or equivalent. Inhaled and topical steroids are allowed.
- Administration of long-acting immune-modifying drugs at any time during the study period (e.g. infliximab).
- Chronic use of antibiotics with anti-malarial effects (e.g., tetracyclines for dermatologic patients, sulfa for recurrent urinary tract infections, etc.).
- Planned administration/administration of a vaccine not foreseen by the study protocol in the period within seven days of Day 1 (for P-Fx and NP-Fx groups) or the malaria challenge (for infectivity control subjects).
- Concurrently participating in another clinical study, at any time during the study period, in which the subject has been or will be exposed to an investigational or a non-investigational vaccine/product (pharmaceutical product or device).
- Seropositive for HIV, HBsAg or HCV.
- Planned travel to malaria endemic areas during the study period.
- Any confirmed or suspected immunosuppressive or immunodeficient condition, based on medical history and physical examination.

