4.2.3.1. Excluded subjects

A subject will be excluded from the PPS and the APPS analysis under the following conditions

Code	Condition under which the code is used	Visit (timepoints) where the code is applicable	Applicable for analysis set
800	Fraudulent data	All	PPS, APPS
900	Invalid informed consent or fraudulent data	All	PPS, APPS
1030	Study vaccine not administered at all	All	PPS, APPS
1040	Administration of concomitant vaccine(s) forbidden in the protocol 
 • Any investigational or non-registered vaccine other than the study vaccines used during the study period. • A vaccine not foreseen by the study protocol administered during the period starting seven days before each dose and ending seven days after each dose of vaccines administration. 	All	PPS
1070	Vaccination not according to protocol 
 • Administration not according to protocol for reason specified by the investigator, other than side, site and route. 	All	PPS, APPS
1080	Good Manufacturing Practice No-Go: Vaccine temperature deviation	All	PPS
1090	Expired vaccine administered	All	PPS
2010	Protocol violation (inclusion/exclusion criteria) 
 • Eligibility criteria not met with an impact on immunogenicity or efficacy data 	All	PPS

Code	Condition under which the code is used	Visit (timepoints) where the code is applicable	Applicable for analysis set
2040	
Administration of any medication forbidden by the protocol
 
 Any investigational or non-registered product drug other than the study vaccines used during the study period. Immunosuppressants or other immune-modifying drugs administered chronically (i.e. more than 14 days in total) during the study period. For corticosteroids, this will mean prednisone ≥ 20 mg/day (for adult subjects), or equivalent. Inhaled and topical steroids are allowed. Long-acting immune-modifying drugs administered at any time during the study period (e.g. infliximab). A vaccine not foreseen by the study protocol administered during the period starting seven days before dose and ending seven days after the dose of vaccine administration. Immunoglobulins and/or any blood products administered during Drugs known to have anti-Plasmodium properties, used during the challenge period before identification of parasitemia 	All	PPS

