8. CHANGES FROM PLANNED ANALYSES

Not applicable.

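### Routine vaccines within seven days of the booster do not eliminate a subject under protocol 7.6.2, but SAP codes 1040 and 2040 exclude that subject from the PPS.

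*Protocol*

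**What the plan says.** **Protocol 7.6.2** lists products that may affect a subject's per-protocol evaluability. One is an unforeseen vaccine given from seven days before to seven days after the dose. Two limits follow that bullet. A footnote lets the window be reduced for a licensed vaccine used in an emergency mass vaccination, with written sponsor approval. Then comes the exemption for routine vaccines: "Although vaccination with routine recommended national vaccination such as with the influenza or pneumococcal vaccines will not lead to elimination". For these the protocol asks only that every effort be made to keep them outside the window.

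**SAP 4.2.3.1** introduces its code table with "A subject will be excluded from the PPS and the APPS analysis under the following conditions". Two rows then cover the same vaccine window:

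- Code 1040: "A vaccine not foreseen by the study protocol administered during the period starting seven days before each dose and ending seven days after each dose".
- Code 2040, the row for forbidden medication: "A vaccine not foreseen by the study protocol administered during the period starting seven days before dose and ending seven days after the dose".

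Both rows are marked as applying to the PPS only. Neither mentions routine vaccines or the emergency reduction.

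**SAP section 8**, on changes from planned analyses, reads "Not applicable".

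**Protocol 5.3**, an entry criterion, covers a related window, again without an exemption: "Planned administration/administration of a vaccine not foreseen by the study protocol in the period within seven days of Day 1". For infectivity controls its window is set around the malaria challenge.

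Protocol 11.9 and SAP 5.3.1 both place the efficacy analysis on the PPS.

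**The concern.** Two documents govern membership of the primary efficacy set, and they give different answers for the same subject. The protocol keeps a booster recipient who has a routine vaccine inside the window. The SAP code table, applied as written, removes that subject even though the subject was challenged and has a valid slide outcome. The protocol says evaluability may be affected; the SAP says the subject will be excluded. The SAP does not declare the difference.

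Timing adds to the problem. The trial is open-label, and an interim efficacy analysis on the Adapted PPS precedes the final PPS analysis (SAP 7.1 and 7.2). If the discrepancy is noticed only when the final sets are built, it will be settled with the slide results already known. With about 20 subjects per group, each affected vaccinee is 1/20 = 5% of the group.

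**Working it through.** **1. The passages side by side, for a vaccinee given influenza vaccine on Day 5 (booster on Day 1)**

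| Source | Window | Routine-vaccine exemption | Emergency reduction | Result |
|---|---|---|---|---|
| Protocol 7.6.2 | 7 days before to 7 days after the dose | Yes | Yes | Kept in PPS |
| SAP code 1040 | Same | None | None | Out of PPS |
| SAP code 2040 | Same | None | None | Out of PPS |
| SAP codes 1040 and 2040, Adapted PPS | Not applied | – | – | Not removed by these codes |

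Outside the seven-day window the passages agree.

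**2. Inputs for the size**

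Protocol 11.4 assumes 19/20 controls and 6/20 vaccinees infected. Protocol 11.9 defines VE as 100 × (1 − relative risk) and specifies two-sided tests at 5%. The documents do not say how many subjects will have a routine vaccine in the window. I take 0 to 3 per group of 20 as an assumption.

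**3. The plan's own figures**

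VE = 1 − (6/20)/(19/20) = 1 − 0.300/0.950 = 68.4%, matching the protocol's approximate 68%. Power is the sum, over all outcomes with Fisher p < 0.05, of the product of the two binomial probabilities (20 at 0.95; 20 at 0.30). It comes to 99.7%, against 99.1% in the protocol table, which is close enough for this purpose.

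**4. Effect of removing vaccinees at the planning assumption (controls 19/20 throughout)**

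| Removed | Infected/N | VE |
|---|---|---|
| None | 6/20 | 68.4% |
| 1 uninfected | 6/19 | 1 − 0.3158/0.95 = 66.8% |
| 2 uninfected | 6/18 | 64.9% |
| 3 uninfected | 6/17 | 62.8% |
| 1 infected | 5/19 | 1 − 0.2632/0.95 = 72.3% |
| 2 infected | 4/18 | 76.6% |
| 3 infected | 3/17 | 81.4% |

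The largest two-sided Fisher p in this table is about 0.0002 (6/17 v 19/20). Exact power with 19, 18 or 17 vaccinees against 20 controls is 99.8%, 99.6% or 99.4%.

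**5. Lowest-efficacy row of the protocol's table (10/20 infected)**

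VE = 1 − 0.500/0.950 = 47.4%. Removing three uninfected gives 10/17 and VE 38.1%; removing three infected gives 7/17 and VE 56.7%. The largest Fisher p is 0.014.

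**The case against.** The best defence is that the code 1040 row is headed as concerning vaccines forbidden in the protocol, and code 2040 and the PPS definition use similar words. Section 7.6.2 is where the protocol lists concomitant vaccines that bear on evaluability, and a vaccine it says will not lead to elimination is arguably not forbidden. On that reading the SAP was transcribed incompletely and reverses nothing. This softens the conflict but does not remove it. The bullets under each heading state the operative condition and omit the exemption, and a programmer working from the table would exclude the subject.

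Other points for the plan stand. All analyses are labelled descriptive (SAP section 6). The interim efficacy analysis uses the Adapted PPS, to which codes 1040 and 2040 do not apply.

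A reader might go further in three ways that the documents do not support:

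- **That criterion 5.3 itself removes these subjects from the PPS.** Its rule is "If ANY exclusion criterion applies, the subject must not be included in the study", but it is checked at study entry. A strict entry rule can coexist with a lenient evaluability rule, and an unplanned vaccine on Day 5 need not breach it. The PPS definition does require eligibility to be met, but code 2010 acts only on breaches with an impact on immunogenicity or efficacy data.
- **That only vaccinees can be lost.** This is true of the vaccine bullets in codes 1040 and 2040, which are tied to the dose. It is not true of 5.3, whose window for controls surrounds the challenge.
- **That the primary result could change.** This needs a scenario outside the documents. With 13/20 infected (VE 31.6%, p = 0.044), removing two uninfected vaccinees gives 13/18 and p = 0.083. That VE lies below every row of the protocol's table, whose lowest is 47%.

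**Conclusion.** The discrepancy is real and undeclared. Within seven days either side of the booster, protocol 7.6.2 and SAP codes 1040 and 2040 give opposite PPS membership for a subject with a routine vaccine. They can also differ for a subject covered by a sponsor-approved emergency reduction.

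The likely consequence is minor. At the planning assumption, one subject lost moves VE down by 1.6 points (68.4% to 66.8%) or up by 3.9 points (68.4% to 72.3%). Up to three lost leaves significance and power essentially unchanged. This rests on 20 per group, 19/20 controls infected and the assumed 0 to 3 affected per group. The actual number could be zero.

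The point is worth correcting because it concerns the primary set and is cheap to settle in advance. It does not show that the primary conclusion is at risk.

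**What to change.** Before the analysis sets are finalised:

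1. Align SAP codes 1040 and 2040 with protocol 7.6.2 by carrying over the routine-vaccine exemption and the sponsor-approved emergency reduction. If the stricter SAP rule is intended, declare and justify the departure in SAP section 8.
2. Delete the vaccine bullet from code 2040, since code 1040 already covers it.
3. Reconcile criterion 5.3 with 7.6.2, and state in the SAP whether a routine vaccine in the entry window counts under code 2010. No position is taken here on which enrolment rule is right.

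Items 1 and 2 are wording in two SAP rows, or one row plus an entry in section 8. No new data are needed, because protocol 7.6.1 already records concomitant vaccinations from seven days before Day 1 to the last visit. For item 3, clarifying code 2010 is a SAP edit. Changing the wording of 5.3 or 7.6.2 would be a protocol amendment needing IRB/IEC review and approval (protocol 6.1), so that part is not free.

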##### **6.4.1.1. Contraindications to malaria challenge**

The only absolute contraindication to mosquito challenge is pregnancy. If this occurs after immunization but before undergoing challenge, the subject must not be challenged and she will be followed for the duration of the study or pregnancy whichever is longer.

A subject with a minor illness but who does not have fever during the pre-challenge assessment may be challenged at the discretion of the investigator. If the subject is

moderately to severely ill with fever on the day of the challenge, he/she will not be challenged. Challenge can be performed within the time window defined in [Table 6](#) and [Table 7](#), at the discretion of the investigator if the subject becomes well. Subjects who will not be challenged will be followed for the duration of the study.

Any conditions which according to the judgment of the investigator would make the challenge unsafe.

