#### *Immunogenicity*

- Anti-CS repeat region antibody concentrations at screening, Day 1, prior to challenge (Day 22), 28 days post-challenge (Day 50) and at study end (Day 190).
- Anti-HBs IgG antibody concentrations at screening, Day 1, prior to challenge (Day 22), 28 days post-challenge (Day 50) and at study end (Day 190).

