## 11.10. Analysis of immunogenicity

The analysis of immunogenicity will be performed on the PPS for analysis of immunogenicity and efficacy.

For each group, at each timepoint where a blood sample is collected:

- The percentage of subjects with seropositive levels of anti-CS (proportion of subjects with anti-CS antibody concentrations  $\geq 1.9$  EU/mL) with 95% CI will be determined at specified blood sampling timepoints. Anti-CS antibody concentrations will be summarized by GMC. Anti-CS antibody concentrations will be displayed using reverse cumulative curves (RCCs). Similar analysis will be performed for the anti-full length CS protein (proportion of subjects with anti-CS antibody titers  $\geq 200$  1/DIL) and anti-C-term antibodies (proportion of subjects with anti-CS antibody concentrations  $\geq 100$  Endpoint Titer).
- The percentage of subjects with seroprotection levels of anti-HBs (anti-HBs antibody concentrations  $\geq 10$  mIU/mL) with 95% CI will be determined at specified blood sampling timepoints. Anti-HBs antibody concentrations will be summarized by GMC. Anti-HBs antibody concentrations will be displayed using RCCs.
- Anti-CS, anti-full length CS protein and anti-CS avidity index will be summarized by mean, SD, median and quartile and box and whiskers plots will be generated.

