4.1.4. Per-protocol set for analysis of immunogenicity and efficacy

The Per-Protocol Set (PPS) for analysis of immunogenicity and efficacy will include all subjects included in the ITTS who fulfilled all eligibility criteria and received the Fx dose according to protocol procedures, did not use any medication, vaccine or blood products forbidden by the protocol, did not report any underlying medical condition influencing the efficacy response, had available data concerning immunogenicity endpoint measures, and underwent *P. falciparum* challenge. This will include subjects for whom assay results are available for antibodies against at least one study vaccine antigen after Day 1.

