2050	Underlying medical condition forbidden by the protocol which may influence the efficacy endpoints	All	PPS
2080	Subjects did not comply with challenge schedule (see Tables 1)	All	PPS
2090	Subjects did not comply with blood sample schedule (see Tables 1)	All	PPS
2100	Serological results not available for all visits for anti-CS	All	PPS
2120	Obvious incoherence or abnormality or error in immunogenicity (antibody) data	All	PPS
3000	Subject did not undergo challenge	All	PPS, APPS

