5.3. Efficacy

5.3.1. Analysis of efficacy planned in the protocol

The analysis of efficacy will be performed on the PPS for analysis of immunogenicity and efficacy.

Efficacy will be assessed by comparison of *P. falciparum* parasitemia incidence and time-to-onset of *P. falciparum* parasitemia after sporozoite challenge. The analysis of the primary objective will be based on blood smears results; additional exploratory analyses will be performed based on PCR results (tertiary objectives).

Vaccine efficacy (VE) is defined as $100 * (1 - \text{Relative Risk})$. Relative risk of infection and 95% CI will be calculated.

Fisher's Exact test will be used for the comparison of *P. falciparum* parasitemia incidence after challenge between each one of the study groups (P-Fx and NP-Fx) and the infectivity control group.

Kaplan-Meier analysis will be performed on time-to-onset of *P. falciparum* parasitemia, for comparisons between each one of the study groups (P-Fx and NP-Fx) and the infectivity control group, using the log-rank statistic.

The same methodology will be applied for the evaluation of the study groups (P-Fx vs. NP-Fx) versus each other. If there are sufficient evaluable subjects (at least a 1:2 ratio between vaccinated and control groups) to draw some conclusions, descriptive analyses based on initial group assignment versus control will be performed.

All statistical tests will be two-tailed at 5% significance level.

Risk periods

For the analyses of time-to-onset of parasitemia (Kaplan-Meier and log-rank), time-at-risk will start on first day of challenge. Time-at-risk will be censored on Visit 22 (Day 50; 28 days post-challenge), drop-out date, start date of anti-malarial treatment or date meeting an endpoint, whichever occurs first. Time-at-risk will be calculated as: censor date – challenge date + 1.

For the analysis of proportion affected (relative risk), all subjects included in the PPS for analysis of immunogenicity and efficacy will be considered at risk of infection and no censoring or elimination will be applied for subjects not completing the entire protocol defined post-challenge follow-up (Day 50; 28 days post challenge).

Case definition

The following will be used as case definition of *P. falciparum* infection:

Asexual blood stage *P. falciparum* parasite density > 0 detected by blood slide reading (or PCR for tertiary objectives).

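### The only antibody analysis set requires challenge, so a correctly boosted vaccinee can lose valid pre-challenge antibody results for a reason that concerns only the slide result

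*Protocol*

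**What the plan says.** **One set for two purposes.** Protocol 11.10 states: "The analysis of immunogenicity will be performed on the PPS for analysis of immunogenicity and efficacy". SAP 5.4.1 repeats this. SAP 5.3.1 uses the same set for efficacy: "The analysis of efficacy will be performed on the PPS for analysis of immunogenicity and efficacy".

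**Challenge is required.** SAP 4.1.4, like protocol 11.5.3, admits only subjects who "had available data concerning immunogenicity endpoint measures, and underwent" challenge.

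**Exclusion is mandatory and covers the whole subject.** SAP 4.2.3.1 opens its table with: "A subject will be excluded from the PPS and the APPS analysis under the following conditions". The visit column reads All for every code. Code 3000, "Subject did not undergo challenge", removes the subject from both the PPS and the Adapted PPS. Code 2040, forbidden medication, removes the subject from the PPS. Its list includes anti-Plasmodium drugs, limited as in protocol 7.6.2 to those with "properties, used during the challenge period before identification of parasitemia". Protocol 7.6.2 says only that such use may affect evaluability; the SAP makes the exclusion definite.

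**The endpoints start before challenge.** Protocol 11.2 lists "Anti-CS repeat region antibody concentrations at screening, Day 1, prior to challenge (Day 22"), and then Day 50 and Day 190. Anti-HBs has the same timepoints.

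**Unchallenged vaccinees remain in the study.** Protocol 6.4.1.1 says: "Subjects who will not be challenged will be followed for the duration of the study". They also remain in the intent-to-treat set (ITTS), but the ITTS is used only for demographics, exposure and safety (protocol 11.7, 11.8, 11.11; SAP 5.1.1, 5.2.1, 5.5.1).

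**The concern.** The two exclusions protect the slide endpoint. Without challenge there is no slide result, and a drug active against the parasite could make a slide negative for a reason other than the vaccine. Neither consideration touches antibody in serum drawn earlier.

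Because the set is shared and the codes act on whole subjects, a vaccinee who received the booster correctly and gave usable screening, Day 1 and Day 22 samples drops out of the seropositivity rates, GMCs and reverse cumulative curves at those visits. The secondary endpoints that describe the booster response would then rest on fewer subjects than have valid data, in groups planned at about 20 at the smaller end.

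**Working it through.** **1. Does anything in the plan restore the results?**

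| Subject | PPS (final antibody analysis) | Adapted PPS (interim efficacy) | ITTS |
|---|---|---|---|
| Boosted, never challenged | Out (code 3000) | Out (code 3000) | In, but no antibody analysis |
| Challenged, anti-Plasmodium drug before parasitemia identified | Out (code 2040) | In | In, but no antibody analysis |
| Challenged, treated after positive slide | In | In | In |

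The interim analysis does not help. SAP 7.2 has all analyses redone for the final report, and there immunogenicity is run on the PPS.

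**2. The plan's own group size (protocol 11.4).** Inputs: about 100 challenged vaccinees in the primary study, 20% refusal, 20% drop-out, and efficacy of about 68%.

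- Booster study: 100 × 0.80 × 0.80 = 64.
- P-Fx: 64 × 0.68 = 43.5. NP-Fx: 64 × 0.32 = 20.5.

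The stated minimum of about 20 per group reproduces. It is already net of both losses, and it describes the smaller group.

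**3. Cost in precision.** The documents give no count of affected subjects, so the number lost, k, is an assumption. The 95% CI half-width of a mean log concentration is proportional to t(0.975, n−1)/√n.

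| Starting n | k | n left | t/√n | Ratio to no loss |
|---|---|---|---|---|
| 20 | 0 | 20 | 0.468 | 1.00 |
| 20 | 1 | 19 | 0.482 | 1.03 |
| 20 | 2 | 18 | 0.497 | 1.06 |
| 43 | 0 | 43 | 0.308 | 1.00 |
| 43 | 1 | 42 | 0.312 | 1.01 |
| 43 | 2 | 41 | 0.316 | 1.03 |

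If every retained subject in a group of 20 is seropositive, the Clopper-Pearson lower limit moves from 83.2% (n = 20) to 82.4% (n = 19) or 81.5% (n = 18).

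**4. Is the loss related to outcome?** The drug rule stops when parasitemia is identified. A subject who stays slide-negative is therefore exposed to it for 28 days, and one who turns positive for fewer. Take 11 days, inside the 9–12 day average in protocol 6.4.1.5, and assume a constant drug-use rate u per 28 days. The probability of removal is u for a slide-negative subject and 1 − (1 − u)^(11/28) for one who turns positive.

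- u = 5%: 5.0% against 2.0%, a ratio of about 2.5.
- With the planning value of 14/20 slide-negative (protocol 11.4), the slide-negative share of retained subjects becomes 0.70 × 0.95 / (0.70 × 0.95 + 0.30 × 0.98) = 69.3%, against 70%.
- u = 10%: 10.0% against 4.0%, and the share becomes 68.6%.
- If slide-negative subjects had twice the GMC of the others (an assumption), the pooled GMC would fall by a factor of 2^(0.693 − 0.700), about 0.5%, at u = 5%, and by about 1% at u = 10%.

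The ratio looks large, but its effect on the summary is very small. It is smaller still if the pre-patent period is prolonged, as protocol 6.4.1.5 says may happen in incompletely protected vaccinees. At 18 days and u = 5% the removal probabilities are 5.0% and 3.2%, a ratio of about 1.5.

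**The case against.** **A common set is a reasonable choice.** It aligns the antibody tables with the efficacy tables, and SAP 5.4.2 compares protected with non-protected subjects and fits logistic models that need a valid challenge result. This stands for those analyses, and the fix leaves them alone. It is no reason to drop valid pre-challenge results from by-group descriptive summaries.

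**Few subjects will be affected.** Pregnancy is the only absolute contraindication to challenge, a febrile subject who recovers may be challenged within the visit window (protocol 6.4.1.1), and chronic use of antibiotics with anti-malarial effects is an exclusion criterion (protocol 5.3). This stands. All analyses are also declared descriptive (protocol 11.12, SAP 6), and these endpoints are secondary.

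**Stronger readings that a reader might infer, and that the documents do not support:**

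- *Every vaccinee given anti-malarial treatment is removed.* The rule covers only use before parasitemia is identified; treatment after a positive slide does not trigger it.
- *The 20% drop-out implies a loss of 4 in 20, and so an interval 14% wider.* The figure of about 20 is already net of drop-out, and a vaccinee who leaves before Visit 3 has no Day 22 sample to lose.
- *The pre-challenge GMC is materially selected on the later challenge result.* The working shows a shift in the slide-negative share of about one percentage point. Nor is a slide-negative subject who took such a drug known to be protected.
- *Day 50 and Day 190 serum is planned for every unchallenged vaccinee.* Protocol 9.2.1 allows those who become pregnant to continue for safety follow-up only.

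**Conclusion.** The concern holds as a point about data retention. Applied as written, SAP 4.2.3.1 with protocol 11.10 discards valid screening, Day 1 and Day 22 antibody results from correctly boosted vaccinees because of a missed challenge, or because of an anti-Plasmodium drug taken during the challenge period before parasitemia is identified. No other planned final antibody analysis keeps them.

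The effect is modest: an interval about 3–6% wider in a group of about 20, and about 1–3% wider in a group of about 43, on the assumption that 1 or 2 subjects per group are affected. Section 11.4 gives no basis for a larger figure. The argument for change is that valid data for stated secondary endpoints can be kept at little cost. Selection bias should not be the main argument. The primary efficacy analysis and its power are not touched.

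**What to change.** Amend SAP 4.2.3.1 and 5.4.1, and protocol 11.5.3 and 11.10, to define a per-protocol immunogenicity set that is applied by visit and does not require challenge.

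- **By-group antibody summaries at screening, Day 1 and Day 22:** do not apply code 3000, the anti-Plasmodium part of code 2040, or code 2080 (challenge schedule) where its only trigger is that no challenge took place. Do not let code 2090 (sampling schedule) or code 2100 (anti-CS results not available for all visits) remove these results only because a later sample is missing or off schedule. Changing codes 3000 and 2040 alone would not be enough, because code 2080 could still exclude an unchallenged subject.
- **Efficacy, protected versus non-protected comparisons and logistic models:** keep all these codes as they are.
- **Day 50 and Day 190:** show any results actually collected from unchallenged vaccinees, with challenge status identified.

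The cost is wording in both documents and one more analysis-set flag. Denominators will differ slightly between the efficacy and antibody tables, which a footnote can explain. No new data are needed.
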